Appendix

Pre-defined coding scheme for number and type of questions

OPTION 5 scoring sheet

QPL development paper

Published study protocol

PCORI Navigating Surgery Question Coding Manual

General Guidance	2
Step 1: Figure out what to code as a question	2
What DOES count as a question that should be coded for this study?.....	2
What DOES NOT count as a question for this study?	2
What about multi-part questions where there are 2 or more questions included in the same section of text? How many questions does this count as?.....	3
What if the speaker is interrupted while asking a question?.....	3
What do I put in the “Wording of Question” field?.....	3
A note on interpretation, transcription and translation and what counts as a question	3
Step 2: Who said it? Determine the speaker.....	5
Step 3: Code the topic area.....	5
OPTIONS	6
LOGISTICS AND TECHNICAL CONCERNS	8
EXPECTATIONS.....	9
RISKS/COMPLICATIONS.....	10
ADVANCE DIRECTIVES	10
OTHER	11
Step 4: Final check for questions	11

General Guidance

- Do not code more than 2-3 transcripts in a single sitting
- Coding each transcript should take about 15-30 minutes
- After you've finished coding a transcript, do a final check by using the find function in Word (Ctrl-F) to locate question marks (clicking through to view all instances), ensure that you've identified all questions, and labeled speakers correctly

Step 1: Figure out what to code as a question

*What **DOES** count as a question that should be coded for this study?*

- We are only coding questions asked by patients or family members while surgeon is in the room
 - Typically, the transcripts end when the surgeon leaves the room but you may come across a transcript in which a surgeon temporarily leaves a room- this will be noted clearly in the transcript. In this case, do not code questions asked during the surgeon's absence
- It does not matter who the question is directed at, even if it is obvious the question is not directed at the surgeon
- Questions must have a question mark at the end
 - Prior to categorizing each question, questions asked by patients or family members will be identified by a Microsoft Visual Basic program, which will generate a coding sheet containing all questions asked by patients and family members during the T0 surgeon visit.
 - After you have coded the entire transcript, use "Ctrl-F" to skip from question mark to question mark to double check that you haven't missed any questions and have labeled speakers correctly
- If a question is within quotation marks (for example, if a patient is quoting someone else's question), that counts as a question and should be coded for topic area just like any other question
 - Example: "And then others go, 'what are you crazy, you're going to get it fixed?... Why would you even think about getting it fixed?'"
 - This counts as two questions
 - 1) "What are you crazy, you're going to get it fixed?"
 - 2) "...Why would you even think about getting it fixed?"

*What **DOES NOT** count as a question for this study?*

- Do not code questions asked by the surgeon or another member of the clinical care team
- Do not code questions asked by patients or family members when the surgeon is not in the room
- Do not code anything that appears question-like but lacks a question mark at the end. These utterances do not count. The following are NOT questions as they lack question marks:
 - "Is there a possibility of me getting a recording from this, because..."
 - "So in my case, you have to remove it."
 - "I don't know what the plasma is."
- Question marks that appear inside square brackets [?] refer to transcriptionist questions (usually about content that is inaudible or medical jargon) and do not count.
 - For example, the following do not count as questions:
 - [inaudible?]

- [Lovastatin?]
 - “He’s teaching me [lots? 2:49]”
- However, question marks that appear *outside* a square bracket do count as questions.
Example: “Do I have to go back to [REHAB NAME]?”

What about multi-part questions where there are 2 or more questions included in the same section of text? How many questions does this count as?

- The number of questions is based solely on the number of question marks
 - For example, this is 5 questions, each entered as its own row in the coding sheet: “But, I mean, does he make an appointment for this surgery in October? I mean, how far out are you looking? Is it really full? I mean, do you ask for that now, the appointment? Do you . . . cancel?”
- Words like “So?” or “Right?” at the end of another question count as unique questions
 - This is two questions: “So the chances of it opening up again are low? Right?”
 - See Step 3 on how to code the topic area for tag-on words like this

What if the speaker is interrupted while asking a question?

- Again, refer to the question marks for guidance. If they’re briefly interrupted (a few words at most) before finishing the question you may need to combine the two question segments together as shown below:

FAMILY: “It’s not laparoscopic . . .”

DOCTOR: “So . . .”

FAMILY: “. . . option?”

This would be coded as one question, which you would enter in your coding sheet as “It’s not laparoscopic...option?”

- On the coding sheet enter all questions from the beginning of the question to the question mark, regardless of interruptions

What do I put in the “Wording of Question” field?

- Paste the entire question into this field. If there is a 1-2 word question after a more substantive statement, include the whole thing.
 - Example: “Oh, you mentioned that he may have some pain in the L2, L3 area. Both?”
You would paste all of this, not just the “Both?” into the “wording of question” field
- If more than one question is asked in a row, paste each unique question in its own field.
 - Example: “So the chances of it opening up again are low? Right?”
You would paste “So the chances of it opening up again are low?” in one row, and “Right?” in a second, separate row; they are two separate entries.

A note on interpretation, transcription and translation and what counts as a question

- In this manual, we distinguish between *interpretation* and *translation*
 - *Interpretation* is the real-time conversion between spoken Spanish and English. This may be provided by a professional interpreter who is present in the consultation room or via a telephone interpreter service. Family members may also provide interpretation
 - *Translation* is the delayed conversion between Spanish and English provided by a transcriptionist listening to the audio file of the consult

- In a subset of transcripts for this study, a professional interpreter or family member provides interpretation between the patient/family and surgeon
- When coding this content, first consider the directionality of the question
 - DO NOT code/count any questions that are asked by the surgeon and then interpreted by an interpreter or the family back to the patient/family
 - We are only interested in questions posed by patients or family members (either questions they ask the surgeon or ask each other)
 - DO NOT code/count any questions that are posed to the surgeon by an interpreter that were not originally asked by a patient or family member
- For questions asked by patients/family members in Spanish, keep the following in mind:
 - Transcripts are fully translated at time of transcription so you may see content that presents as:
 1. Patient: Asks question in Spanish, shown as Spanish in transcript
 2. English translation of what patient just said, translated by transcriptionist
 3. Family member or interpreter: Interprets Spanish question to English for surgeon
 4. Surgeon: Answers question in English or asks a question to patient in English
 5. Family member or interpreter: Interprets English surgeon answer or question to Spanish for patient
 - The only part of the above exchange that should be coded/collected as a question to be coded is #2. Copy the transcriptionist-provided English version of this question or questions into your codebook
- It is important not to double-count these questions if the same question appears in both English and Spanish in the transcript
 - Do not code/count questions that appear in Spanish in the transcript. Do not count #1 and #3 above as questions for this reason
- It is possible that the interpreter or family member providing interpretation could misinterpret the patient/family question (for instance, condensing multiple questions into a shorter, simpler question). Since we are interested in patient/family member activation and want to count all questions they *intended* to ask we do not want to code the interpretation of their questions, only what they *actually* said, as translated by a bilingual transcriptionist. Transcriptionist-provided translation will appear in brackets or bolded text after the original text, as shown below:
 - Patient: Cuánto dura la operación? Estaré en el hospital por mucho tiempo? **[How long is the operation? Will I be in the hospital long?]**
 - Interpreter: How long will I be in the hospital?

In the example above, this would count as 2 patient questions because the patient asked 2 questions, as translated by the transcriptionist. It is not counted as just one question because we are reliant upon the transcriptionist's translation, not the interpreter's. The same would be true if a family member had been present and translating during the consult and condensed this into one question

- If a professional interpreter is present do not code/count their questions
- If a family member is providing interpretation
 - If the family member is literally relaying a surgeon's questions to a patient, or even relaying but also adding their own content beyond what the surgeon asked, do not count this as a question
 - If the family member is relaying a patient or another family member's question to the surgeon, do count this as question, as the question will separately be coded/collected as shown in #2 above
 - If a family member acting as an interpreter asks their own question to the surgeon, this is coded/collected as any other family member question would be

Step 2: Who said it? Determine the speaker

- Code all questions asked by patients or family members/loved ones while surgeon is in the room
- Do not distinguish between family members – these are all coded as “family member”
 - In some cases, a support person such as a friend may be present. Code their questions as “family member” as well
- If question speaker is unknown, count these as patient questions UNLESS transcriptionist makes a note it's a medical provider (though they are unsure of *which* provider) AND the content of the question indicates that a clinician asked it
- Do not code questions asked by the surgeon, resident(s), or other clinical staff
- Exclude questions asked while the surgeon is not present

Step 3: Code the topic area

Look for content before and after the question to determine its topic area/context. However, do not exclusively base your topic coding on how the surgeon answers the question – it is possible the surgeon may have misinterpreted the question or even ignored it. However, if the conversation seems to be consistently in one line of thought, the surgeon's response may help clue you into what the topic area should be coded as. What the patient says immediately before/after the question may also be helpful if you are struggling to identify the topic area. You may only code each question as having one topic area so carefully review the topic area codes to determine which best fits the question.

There are 6 topic area codes: OPTIONS, EXPECTATIONS, LOGISTICS AND TECHNICAL CONCERNS, RISKS/COMPLICATIONS, ADVANCE DIRECTIVES, OTHER. These are each described in more detail below. But first, here is some guidance on how to handle very short questions.

How should I code the topic area for very short questions?

- Short questions that stand all alone without any text surrounding them on that line of the transcript are always coded as “OTHER” and count as a single question. Examples:
 - “Is that right?”
 - “Really?”
 - “Huh?”
 - “Oh did he?”
 - “You know what I'm saying?”
 - “Oh, yeah?”

- Similarly, short questions that are a reiteration of what was previously said or are purely rhetorical are coded as one question with “OTHER” as the topic area. Examples:
 - “Oh really, two thirds?”
 - “It does, doesn’t it?”
 - “Now what was I going to say?”
 - *Surgeon*: “I’ve trained since 1984, so. So if you, we all do about 200 to 250 operations, 200 to 250 operations a year.”
Patient: “Wow. Since ’84?”
- If a patient or family member asks the same question twice or more with the exact same wording, code the first instance of the question based on its content and code the second/any later instances as “OTHER”. Example:
 - *Patient*: Rehab for 6 weeks? [this would be coded as “EXPECTATIONS”]
 - *Surgeon*: Yeah.
 - *Family member*: Rehab for 6 weeks? [this would be coded as “OTHER”]
 The question must be exactly the same for this rule to apply. If there are minor wording changes, code each question as you would normally. Example:
 - *Patient*: Rehab for 6 weeks? [this would be coded as “EXPECTATIONS”]
 - *Surgeon*: Yeah.
 - *Family member*: ‘He’d be in rehab for 6 weeks?’ [this would be coded as “EXPECTATIONS”]
- Short questions that are attached or directly next to a statement (in the same line of text) that is substantive (not simply re-stating what has already been said) are coded based upon the topic of the statement that precedes the short question. The short question is considered attached to the longer statement to be coded as ONE question. When filling out the coding sheet, include both the statement and the short question. This applies to short questions that are next to a statement and separated either by a comma OR a period
 - “But it’s inside the aorta, right?”
 - This question should be coded as “LOGISTICS AND TECHNICAL CONCERNS”
 - “But it’s in the aorta. No?”
 - This question should be coded as “LOGISTICS AND TECHNICAL CONCERNS”
 - “There’s no nano-technology on it yet. Right?”
 - This question should be coded as “LOGISTICS AND TECHNICAL CONCERNS”
 - “So this seems like my only option, right?”
 - This question should be coded as “OPTIONS”
- Short questions that are attached or directly next to a substantive question count as two questions ALTHOUGH the topic code for each question may be different. Usually, the short question is coded as “OTHER” while the longer question is coded according to the topic
 - “So the chances of it opening up again are low? Right?”
 - This is two questions; the first coded as “RISKS/COMPLICATIONS”, the second coded as “OTHER”

OPTIONS

“What can I do for this problem?” or “Are there other treatments apart from surgery?” are the main sentiments behind this topic area. This code should be used for questions that seek to understand what

the different treatment paths or choices are or to compare treatments. Look for words like: options, choices, alternatives

- Use this code for any questions that reference seeking additional information on possible treatment options including
 - Surgery Choice #1 vs Surgery Choice #2
 - Observation vs Surgery (Observation includes non-surgical alternatives like symptom management/medical treatment)
 - Different approaches to surgery:— open, laparoscopic, endoscopic (e.g. with catheters) (see Appendix A for examples of approaches)
 - Radiation vs chemotherapy
- Use this code for questions that are asking for recommendations: What do you think? What would you recommend?
 - Some requests for recommendations may be subtle and may sound like the patient/family member is asking for reassurance regarding a particular treatment choice
 - For example: “So there’s really no point in putting it off, right?” or “So I’m not a gambling man, but that sounds like a reasonable investment, right?”
- This includes questions about having more options if the patient does something (gains weight, stops smoking, tumor shrinks with chemo) or something happens to allow another option to be available: “If I _____, is this treatment possible?”
- Do not code questions as being “OPTIONS” if they’re about options for other things *within* the major treatment (such as whether to get a blood transfusion during surgery, what type of equipment the surgeon will use, or where an incision is made). These would instead be coded under “Logistics and Technical Concerns”
- “OPTIONS” VS “LOGISTICS” – is it about an option or a technique within an option?
 - *What vs. how* is a good way to distinguish between these two topic areas. Questions asking *what are the options* are coded as “OPTIONS” whereas questions on *how to do it* are coded as “LOGISTICS”
 - If the question is about a treatment *approach* code it as “OPTIONS”. Words that indicate a treatment *approach* is being discussed include: open, minimally invasive, laparoscopic, endoscopic, robotic, endovascular or catheter based approach (includes TAVR/TAVI, EVAR or TEVAR), single incision/single port, or any option that involves interventional radiology instead of surgery
 - However, if a question is about a technique *within* an option, code it as “LOGISTICS”. Techniques include: staples versus stitches/hand sewn, type of stent or catheter, type of graft, and reference to specific equipment/techniques – e.g. lasers, ablation, coagulation devices, ultrasound, ligasure, staplers, fluoro, dilators, scopes, cameras, specific needles or types of sutures
- “OPTIONS” VS. “EXPECTATIONS” OR “RISKS”
 - If a question is *comparing* outcomes/risks/expectations between two or more treatment options, code it as “OPTIONS”. Look for words that indicate the speaker is thinking about the relative value of things (better/worse than)
 - Example: “It’ll give it a better chance?”
 - However, if the question is asking about risks of a procedure, what life will be like within a given treatment, or after a treatment decision has been made, code this as “RISKS” or “EXPECTATIONS”. A question is NOT coded as “OPTIONS” *unless* it seeks to compare two or more options.

- Example: "So I would end up with paralysis if I didn't have the surgery?" [This is coded as OPTIONS because it's focused on *comparing* outcomes between surgery and no surgery]
Example: "How likely is it that I will be paralyzed after surgery? [This is coded as "RISKS" because it is focused on the risks of surgery only]
- "OPTIONS" examples:
 - "What is the difference between the aftereffects of radiation versus chemo as far as...the feeling?"
 - "Is there another way?"
 - "So what alternative do you think would be good?"
 - "If I was your dad, what would your advice be?"
 - "So if I, if I put weight on, and I gain some more weight, that would make a difference?" [asking if they could get a specific surgery if they put weight on]
 - "So this seems like my only option, right?"

LOGISTICS AND TECHNICAL CONCERNs

Questions about how things will work up to and through surgery. Once they hit the post-operative stage, those questions go under "EXPECTATIONS". Use the time period in the question as your guide on when to use this code.

This code includes a broad range of questions about technical or logistical aspects of surgery/treatment but also the health condition itself: Why do I have this? What's going on here?

- Includes any questions that reference surgical instruments, length of surgery, medications, surgeon expertise, surgeon practice patterns, surgical technique or procedure (see Appendix A for examples of techniques) surgery names and technique names, locations on surgery day, pre-op instructions, timing issues
- Includes specific questions about anatomy and physiology*, surgery, medications, blood products, surgeon expertise, institutional quality/expertise** practice patterns (who actually does the surgery, how many times per year this surgeon does it, etc.)
 - * These changes may include things such as cell or organ level functions/changes. Questions about physiological or anatomical changes *up to and during* the treatment are coded as logistics. Questions about these changes occurring *following* treatment are coded as expectations.
 - **Sometimes people ask about other institutions (like Mayo Clinic) but their question is not really about going there or the logistics of having treatment at another institution. What they're really asking about it is whether the procedure they do there could be done here. In this case, the question should be coded as "OPTIONS". Read questions asking about other institutions carefully as they could fall under logistics or options.
- Includes questions on location of providers and services only if they relate to the health condition and treatment being discussed
 - Example: "Is it here in this building?" would be coded as "LOGISTICS" if it's a question of where the patient's loved ones would wait for them during surgery.
 - If it was a question about where another doctor practices who is not involved in their care for the health condition being discussed with the surgeon, this would be coded as "OTHER".

- For example, if a patient and surgeon are discussing the town the patient lives in and the patient says, “Oh do you know, Dr. X? He’s my neighbor! Do you know where he works?” without any reference to Dr. X being involved in their care, this would be coded as “OTHER”.
- Includes questions about other doctors or medical personnel but only when they are related to the health condition prompting the surgical consult (questions such as “Should I let my PCP know I’m scheduled for surgery?” should be coded as “LOGISTICS” but questions about other doctors unrelated to the condition being discussed are coded as “OTHER”- an example of this would be “Do you know Dr. X?” where there is no connection between Dr. X and their condition described)
- “LOGISTICS AND TECHNICAL CONCERNs” examples:
 - “How long does the surgery take?” or “Any idea of timing?” [When will surgery be?]
 - “How will blood drain from...after you take the vein out?”
 - “Is this something like, this is not uncommon for you people?”
 - “So how many bypasses are there?”
 - “Yeah, how long do you think this has...?” [referring to discussion of blockages building up]
 - “Do you work with him a lot?” [Though note that this is coded as “LOGISTICS” only if it’s asking about a doctor involved in the treatment of their condition being discussed with the surgeon. If this was about a doctor unrelated to the health condition being discussed, this would be coded as “OTHER”]
 - “But that other way is easier to get to? [This is coded as “LOGISTICS” as opposed to is there another option]”
 - “Which valve?”
 - “What does TAVI stand for?”

EXPECTATIONS

Questions about what will happen AFTER surgery, including in the immediate, post-operative period right after surgery. Use the time period in the question as your guide on when to use this code- it must relate to something after surgery. “If we do this, what’s gonna happen after surgery?” is the main point of this topic area.

This topic area includes questions that seek to understand how the patient’s life will change or remain the same following a specific treatment option, particularly in terms of quality of life and patient reported outcomes. Look for words like: feeling, after-effect.

- Includes patient reported outcomes such as quality of life, recurrence, changes in energy levels, mobility, continence, scarring, wound-care, bags/drains/tubes after surgery, rehab details, recovery time, limitations in function or other capacity, durability of procedure (for example how long will my new heart valve last?), length of hospital stay after surgery,
- Note: questions about the length of the surgery or procedure are coded under logistic/technical concerns, NOT expectations because this question relates to the procedure itself, not what happens after
- Note: questions about physiological or anatomical changes *following a treatment* are coded under EXPECTATIONS. These changes may include things such as cell or organ level functions/changes

- “EXPECTATIONS” examples:
 - “Like, you know, how long will be the recovery?”
 - “Like my nose going to be running all the time or?”
 - “Right, but would there be any additional pain?”
 - “It like, I mean, do you have a timeline historically when it would start to . . . regenerate again or grow again?”
 - “These are maybe questions for later, but since they're on my mind now, when can he take aspirin again?”
 - “After the two weeks [post-op] or even during those two weeks, can he go visit him or not?”
 - “So how long would he need somebody with him kind of 24 hours after he gets home?”

RISKS/COMPLICATIONS

This topic area includes questions that seek to understand what could go wrong during or following the treatments options that are being discussed (operating, not operating, chemo, radiation, etc.)

Technical discussion of near-term, surgeon-defined complications (e.g. 30 days). Look for words like: risks, complications, chances, odds. Note that this includes the risks of not operating as well as risks associated with surgery or other treatment options.

- Include any questions that reference short-term, surgeon defined effects from treatment including extended hospital stay, extended recovery time, blood clotting, bleeding, etc.
- “RISKS” VS “EXPECTATIONS” code: Code any questions that reference long-term effects/outcomes including recurrence, durability of procedure as “EXPECTATIONS”, not “RISKS”
 - Be careful about the context: is the patient specifically asking about *how it's going to get done* or about *bad outcomes*? (*How it's going to get done* would go under “LOGISTICS AND TECHNICAL CONCERNS”—even if it's serious or dangerous. Whereas questions on *bad outcomes* are coded as “RISKS”)
 - If the question is *comparing* risks of two or more treatment options, code this as “OPTIONS”
- “RISKS/COMPLICATIONS” examples:
 - “How many people have to be on a ventilator after?”
 - “As far as the location of the tumor that remains in those veins and stuff, is everything, is anything at risk as far as, I don't know, blood flow function of any of those parts?”

ADVANCE DIRECTIVES

This topic area includes questions that seek information on options or preparation in the case that the patient cannot speak for him/herself. It also includes any questions that are part of a discussion of advanced care planning. This includes questions that express a preference about kinds of health states you might talk about in an advance directive: life sustaining medical treatment, feeding tubes, serious stroke, lack of independence. Look for words like: DNR, Power of Attorney (POA), living will, advance directives.

- If they are expressing preferences about what should be done if a bad outcome occurs, code this as “ADVANCE DIRECTIVES”. If they are merely discussing the risk/complications related to a surgery (likelihood of them happening), code it as “RISKS/COMPLICATIONS”.
- “ADVANCE DIRECTIVES” examples:
 - *Doctor:* “Yeah. Well if something goes terribly wrong, you’re, and you’re not able to even communicate with us, I’m assuming your wife would answer for you, and not, not, not, she would express to us what your wishes would be. I mean, normally I wouldn’t keep people going, sort of, inappropriately on life support. I think that’s a cruel thing to do.”
 - *Family Member:* “Then, you know, why continue?”
 - “What if I can’t talk after surgery, how can I make sure someone knows what I want to be done?”
 - “How do I set it up so my wife can make decisions for me if something goes wrong?”

OTHER

This topic area includes the following types of content:

- Sometimes very short questions like “Right?” are coded as “OTHER”. See guidance at the beginning of this section on how to code the topic area for very short questions
- Questions that refer to something about the patient’s health that do not fit in any of the other categories (e.g. Genetic testing, complications of *past* procedures, family history and health of others)
- Includes questions about other doctors or medical personnel *unrelated to the treatment of the health condition prompting the surgical consult*
- Includes questions on location of providers and services if they are NOT related to the health condition and treatment being discussed
- Non-health questions:
 - “Do you mind if I write too?”
 - “How many grandkids do you have?”
 - “Are you writing with a fountain pen?”
 - “Wow, you typed all of these files?”
 - “Are you in favor of this being recorded?”
 - “You need some water?”

Use caution in applying this code – do not use it as a catchall when you’re unsure of the topic area code.

Step 4: Final check for questions

Once you have read through the transcript and coded each question, go through and review to ensure that you didn’t miss any questions. This is a critical step as it is all too easy to miss a question.

Starting from the beginning, hit “Ctrl+F” to find all of the “?” marks in the transcript. Compare the questions highlighted in the transcript to the questions you have indicated on your coding sheet. Make sure you only included questions from the patient and/or family member(s), and that you have labeled the speakers correctly.

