The intervention effect will be tested in the framework of generalized linear mixed effects models^{42,43} with a treatment dummy variable, surgeon random effect and site-by-time dummy variables to control site-specific secular trends.

All models will be estimated and tested using SAS version 9.3 (SAS Institute, Cary, NC), specifically PROC MIXED and PROC NLMIX.

We do not plan to impute missing data if the rate of missingness is low. Currently, our rate of missingness is quite low: 97% of patients and 92% of family members have completed T1. For T2, 88% of patients and 86% of family members have completed the survey and for T3 87% of both patients and family members have completed their survey. We plan to exclude variables for which there is no response (rather than impute these variables). Although we have a small number of incomplete audio recordings, we will treat audio recordings where less than half of the encounter with the surgeon was captured (a total of 6 recordings) as completely missing and those with more than half recorded as complete. We will perform sensitivity analysis to test whether this small loss of data impacts our findings by comparing the outcomes with and without inclusion of audio recordings that are more than half complete.

Aim-1 primary outcomes [Question Counting, PEPPi-5]

Aim 1 has five primary outcomes and as such will be analyzed with a Type I error rate of $\alpha=0.01$.

For question counting, we consider four specific types of questions and evaluate them with ordinal categories:

- Number of OPTIONS questions asked by patients and family members (0, 1, 2+)
- Number of EXPECTATION questions asked by patients and family members (0, 1, 2+)
- Number of ADVANCE DIRECTIVES questions asked by patients and family members (0, 1+)
- Number of RISKS questions asked by patients and family members (0, 1, 2+)

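### The question coding manual gives opposite orders on a family member's relay of a patient's Spanish question; read literally, a reworded relay can move a visit from 1 to 2+ on three of the four question-type endpoints

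*Combined protocol and SAP*

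**What the plan says.** The manual sets out a Spanish-language exchange in five steps. Step #1 is the patient's question in Spanish, #2 is the transcriptionist's English translation, and #3 is the spoken relay: "Family member or interpreter: Interprets Spanish question to English for surgeon". The rule that follows is firm: "The only part of the above exchange that should be coded/collected as a question to be coded is #2". The purpose is also stated: "It is important not to double-count these questions if the same question appears in both English and Spanish in the transcript". The order on the relay is explicit: "Do not count #1 and #3 above as questions for this reason".

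A few lines later, in the bullets for visits where a family member interprets, the manual takes up a relative who passes on a patient's or another relative's question to the surgeon. Here it says: "do count this as question, as the question will separately be coded/collected as shown in #2 above". For a patient's Spanish question, this is the same event as step #3.

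Step 3 of the manual also has a rule for repeats. A later instance of a question is coded Other, but "The question must be exactly the same for this rule to apply", and "If there are minor wording changes, code each question as you would normally".

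The counts feed the Aim 1 primary outcomes. Options, Expectations and Risks are analysed as 0, 1 or 2+, and Advance Directives as 0 or 1+ (Aim-1 primary outcomes; repeated in the modified plan). Under Data coding, each transcript has one coder for question categories.

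**The concern.** Two instructions in one note give opposite orders on one utterance. The bullet's reason, that the question is already collected under #2, is a reason to leave the relay out, so a dropped negative is likely. The neighbouring bullet, on relayed surgeon questions, does carry the negative.

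The top category of three primary endpoints starts at two questions, so a single extra row is enough to change a visit's category. The other controls would not reliably remove that row:

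- The repeat rule catches only identical wording.
- The extraction program lists questions asked by patients and family members, and a relative's relay that ends in a question mark fits that description.
- The final check in Step 4 confirms that the speaker is a patient or relative and is labelled correctly. A relay passes both tests.
- With one coder per transcript, no second coder would expose a different reading of the rule.

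**Working it through.** The plan states no figure on this point, so there is none to reproduce. The check is to apply the rules to an exchange and then to illustrate the scale.

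**1. One Spanish question and one family relay.** Assume that the relay ends in a question mark and gets the same topic code as the question it repeats.

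| Relay counted? | Relay wording compared with #2 | Count for the topic | Options, Expectations, Risks | Advance Directives |
|---|---|---|---|---|
| No (step list) | any | 1 | 1 | 1+ |
| Yes (later bullet, literal) | identical | 1 (repeat goes to Other) | 1 | 1+ |
| Yes (later bullet, literal) | reworded | 2 | 2+ | 1+ |

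Only the last row differs, and only for the three endpoints scored 0, 1, 2+.

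**2. The manual's own example.** The patient asks in Spanish about the length of the operation and about the length of the hospital stay. The interpreter condenses these into one differently worded question about the stay. The manual counts two questions, and says that the same would hold if a family member had done the translating. Under its topic rules, length of surgery is Logistics and length of hospital stay is Expectations.

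- Step list: Logistics 1, Expectations 1. The visit is in Expectations category 1.
- Later bullet taken literally, with a family member relaying: Logistics 1, Expectations 1 + 1 = 2. The visit is in Expectations category 2+.

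So the literal reading of the bullet contradicts the worked example as well as the step list.

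**3. Scale, on assumed inputs.** The manual says that interpretation occurs in a subset of transcripts and does not give its size. Nor do the documents give the share of visits with exactly one question of a type. Inputs:

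- N = 222 + 221 = 443 visits (Updated analysis plan and modified power analysis).
- s = share of visits with a reworded family relay that the coder counts. Assumed 1% to 10%.
- P(1) = share of visits with exactly one question of a given type. Assumed 10% to 30%.

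Visits moved from 1 to 2+ = N × s × P(1):

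- Low: 443 × 0.01 × 0.10 = 0.4 visits (0.1 percentage points).
- Middle: 443 × 0.05 × 0.20 = 4.4 visits (1.0 point).
- High: 443 × 0.10 × 0.30 = 13.3 visits (3.0 points).

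For a given s and P(1), each result is a ceiling, because it takes the single question of that type to be the one that was relayed.

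**The case against.** The strongest reply is that the bullet has a consistent reading. The bullets under family interpretation contrast whose question is being relayed: a surgeon's question never counts, while a patient's or relative's does. If the word for what is counted refers to the patient's question, the clause says that it counts and that this happens through #2. No second row then arises, and the reason fits. The surrounding text supports that intent several times over: only #2 is to be coded, double counting is warned against, the interpretation itself is said not to be of interest, and the worked example is extended to family interpreters. A careful coder could well have followed it, and the documents do not show that anyone entered a duplicate row. This stands, and it limits the point to an ambiguity with a possible consequence.

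The exposure is also narrow. Professional interpreters' questions are clearly excluded. The relay must come from a relative, end in a question mark and be reworded. The visit must have exactly one question of that type, and the coder must prefer the bullet to the step list. All of this stands.

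A reader might infer a biased treatment effect. The documents do not support that. Coders are blinded and receive an even mix of arms (Blinding), and the model has a surgeon random effect and site-by-time terms. One route to a difference is conceivable: under Family member presence, the plan says that the question list may prompt patients to bring a relative, and only relatives' relays fall under the bullet. That is a possible mechanism, not evidence of a difference. Clustering at sites or surgeons with more Spanish-speaking patients is likewise a reasonable inference without a documented figure.

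**Conclusion.** The contradiction is real and stands in the current text of a coding rule for primary endpoints. Taken literally, the bullet produces the double count that the same note forbids, and a reworded relay can move a visit from 1 to 2+ on Options, Expectations or Risks. Advance Directives cannot move, nor can the planned composite, which treats each question type as asked or not asked.

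The size is unknown and probably small. The 0.1 to 3.0 percentage points per question type rest wholly on assumed shares and are ceilings within those assumptions, so they should not be read as an estimate of misclassified visits. Two stronger conclusions are tempting: that duplicate rows were entered, and that the comparison between arms is distorted. The documents establish neither. This is a clarification worth making, not a threat to the primary analysis.

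**What to change.** Reword the bullet so that it agrees with the step list: when a family member relays a patient's or another relative's question, do not count the relay, because the question is already collected under #2.

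Before unblinding, check the coding sheets of transcripts that were flagged as containing a language other than English and in which a family member interpreted. Remove any row that duplicates a question already entered from the transcriptionist's translation, and record how many rows were removed and for which question types.

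The cost is one corrected clause and a review of a small subset of sheets. The subset can be found from the language variable in Table 4, and the sheets hold the full wording of each question. The plan completes all coding before unblinding, so the check can be done blind to arm and needs no change to the analysis models.
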